## **8 Study Compliance**

- A. See study compliance doc [redacted]**

## **9 Data Collection and Study Forms**

### **9.1 Participant Binder**

- A. See BRIEF Recruitment Logs**

### **9.2 Study Forms**

- A. See Aim 3. BRIEF Intervention shared drive for study forms**

### **9.3 General Instructions for Completing Forms**

### **9.4 Data Flow**

- A. See analysis plan**

### **9.5 Administrative Forms**

- A. See Aim 3. BRIEF Intervention shared drive for administrative forms**

## **9.6 Retention of Study Documents**

### **10 Data Management**

#### **10.1 External Data**

#### **10.2 Quality Control Procedures**

##### **10.2.1 Standard Operating Procedures**

##### **10.2.2 Data and Form Checks (as appropriate)**

### **11 Concomitant Medications – Drug Intervention studies only**

### **12 Data and Safety Monitoring Activities**

#### **A. Data Security**

- a. Level 3: Could cause risk of material harm to individuals if disclosed.
  - i. Description: These data could result in harm that can have genuine impact, but the magnitude and/or duration are generally not serious, long-lasting, and/or irreversible.
- b. See [GUIDANCE\\_Data\\_Security\\_Protections\\_1.31\\_2021.06.24](#) for additional details

#### **12.1 Study Completion and Close-Out**

##### **12.1.1 Participant Notification**

#### **A. To be developed upon completion of analysis**

##### **12.1.2 Confidentiality Procedures**

##### **12.1.3 Publications**

### **13 MOP Maintenance**

Better Research Interactions for Every Family

Statistical Analysis Plan

Project # 3469

[name]

6/1/2022

A feasibility study for an educational intervention to improve equity and respect in recruitment conversations with families who are eligible for a neonatal clinical trial. A pre-post study design will be used. Approximately 200 parents of eligible infants will be approached for consent, half using the current recruiting protocol ("pre") and half using the novel intervention ("post"). Conversations will be administered by 6 members, some of whom will administer more conversations than other members.

A subsample of these conversations will be recorded (n_record). This will be split equally between "pre" and "post" periods. Each recorded recruitment conversation will then be assessed by 3 experts (2 independent, and the member who administered the educational content). They will fill out a questionnaire (approximately 15 questions) answered with a Likert score. These questions fit into logical groupings to assess different aspects of equity and respect during the recruitment conversation.

The number of observations will be the number of conversations recorded multiplied by 3 (n_record*3). There are several sources of correlation between these observations (recruitment conversation, member administering the recruitment conversation, expert making the assessment) and so GEE will be used to estimate the intervention effect on each question and test the null hypothesis of no effect.

Analysis Plan

Descriptive statistics will be used to summarize eligible parents who engaged in conversations. Frequencies and percentages will be reported as appropriate for categorical variables. Means, medians, and standard errors will be calculated for continuous variables. Outcomes (5-point Likert scale) will be summarized in each intervention arm at the question level, as a total across all questions, and totals within each pre-defined question subgroup.

At the question level, ordinal logistic regression will be used to assess the effect of the intervention on the distribution of scores. Models will be fit using generalized estimating equations (GEE) to account for correlation among results assessed on the same conversation. Results will be reported as intervention odds ratios and 95% confidence intervals. To test the overall effect of the intervention on the score (and in each subgroup of questions) we take the total of the question scores to be continuous and use GEE to fit standard linear regression to test the mean effect of intervention.

Models above assume each conversation administer has the same mean outcome and that experts evaluate themselves the same as others. These two assumptions will be evaluated and GEE models adjusted as needed. Further, since we plan to run many statistical tests (15 questions individually, score totals, subgroups), the p-value threshold to determine significance will be adjusted using Holm's method to control the family-wise type I error rate.

List of Figures/Tables

Figure 1: Flow diagram showing sample size allocation in pre/post cohort, exclusion, and number of videos sampled for assessment.

Figure 2: Distributions of scores in pre/post cohorts for each question, question totals and subgroups.

Figure 3: Estimated odds ratios and confidence intervals and of the pre/post effect tested for each question.

Table 1: demographics of those approached vs videos sampled.

Table 2: Likert score outcomes (counts, percentages) in pre/post, intervention odds ratio, 95% CI's and p-values for each question.

Table 3. Outcome totals (Mean, SD, IQR) and subgroups, estimates of mean effects (95% CIs) .

Power calculations

To assess statistical power, we pair simulation with calculations based on cluster randomized trial designs with a continuous outcome. These equations assume a mixed effects model consistent with the GEE methods used above and depend on the assumed effect size, outcome standard deviation, and intra-cluster correlation. To achieve 80% power at a 0.05 level when the true mean difference is 5 and standard deviation of 5, 8 videos (with 3 observations) need to be recorded per trial arm ($8*3*2 = 48$ total observations) if the intra-recording correlation is low ($\rho = 0.1$) while 15 recordings are needed per trial arm ($15*3*2 = 90$ total observations) if intra-recording correlation is high ($\rho = 0.8$).

Input parameters were selected based on simulated ordinal 5-level data (with a uniform distribution across levels) generated 15 times (one for each question) to get totals across many realizations. This leads to an approximate distribution of total scores with mean 45 and standard deviation 5.

References

Heagerty, P.J. and Zeger, S.L. (1996) Marginal regression models for clustered ordinal measurements. *JASA*, **91** 1024–1036.

Matthews JNS. Introduction to Randomized Controlled Clinical Trials (2nd Ed.) Chapman & Hall: New York, 2006.

Donner A and Klar N. Design and Analysis of Cluster Randomization Trials in Health Research. Arnold: London, 2000.

Holm, S. (1979). A simple sequentially rejective multiple test procedure. *Scandinavian Journal of Statistics*, **6**, 65–70.
<https://www.jstor.org/stable/4615733>.

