## **2 Brief Overview of the Study Protocol**

**A.** The goal of this study is to pilot test the feasibility of implementing a modified recruitment approach, the Better Research Interactions for Every Family (BRIEF) Intervention, within a neonatal clinical trial. This intervention has two distinct aims: 1) improve the experience for parents asked to enroll their infant in a neonatal clinical trial; 2) decrease disparities in enrollment within a neonatal clinical trial. We will apply the BRIEF Intervention within a single site neonatal randomized control trial (RCT), the Darbe plus IV iron study, using pre/post approach. The objectives of this current ancillary study are to assess feasibility, gain preliminary experience to drive further refinement, and provide effect estimates for a future RCT of the BRIEF intervention.

This study is an ancillary study to the Darbe plus IV Iron study, which is a phase II RCT aiming to demonstrate the feasibility and potential benefit for darbepoetin plus slow-release intravenous iron to decrease transfusions, maintain iron sufficiency, and improve neurodevelopmental outcomes of preterm infants. In the BRIEF study, we will pilot a research team educational module to support recruitment for this neonatal clinical trial.

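### The non-randomised pre/post models have no case-mix or time term, and no listed output compares the parents in the two periods, so a period change could be reported as intervention effect

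*SAP*

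**What the plan says.** - **Design.** The protocol (section 2) applies the intervention inside a single-site trial "using pre/post approach", and the SAP's opening description agrees: "A pre-post study design will be used". About 200 parents are approached, half in each period. The protocol gives effect estimates for a later RCT as one objective.
- **Recruiters.** "Conversations will be administered by 6 members, some of whom will administer more conversations than other members".
- **Question-level model (SAP, Analysis Plan).** "ordinal logistic regression will be used to assess the effect of the intervention on the distribution of scores", fitted by GEE and reported as odds ratios for the intervention.
- **Total-score model.** The SAP will "use GEE to fit standard linear regression to test the mean effect of intervention". Neither model lists a parent or infant covariate or a time term.
- **Recruiter assumption.** "Models above assume each conversation administer has the same mean outcome". The SAP will check this, together with the assumption about experts rating themselves, and adapt the GEE models where needed. It gives no criterion.
- **Outputs (SAP, List of Figures/Tables).** "Table 1: demographics of those approached vs videos sampled". Figure 1 gives numbers by cohort; Figure 2 and Table 2 give scores by cohort. None is listed as giving parent characteristics by period.
- **Recordings.** The SAP leaves the number open and powers the study on 8 or 15 per arm. Protocol section 7.4 plans 100, which is 50 per arm if split equally as the SAP intends.

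**The concern.** Without randomisation, the period coefficient is the training effect plus whatever else differed between the periods. Two sources are plausible here. The mix of families approached may change, and so may the mix of those who agree to be recorded. Six recruiters sharing about 200 conversations may also improve with practice. The models cannot separate either source from the training, and the listed tables would not let a reader see the first.

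The SAP goes beyond description: it tests a null hypothesis of no effect, with family-wise error control. That control deals with the number of tests, not with confounding by period. A shifted estimate would pass unmarked into the planning of the later RCT.

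**Working it through.** **Inputs from the SAP (Power calculations).** Difference 5, SD 5, m = 3 ratings per recording, 5% level (two-sided assumed), 80% power; 8 per arm at rho 0.1 and 15 per arm at rho 0.8. The 50 per arm comes from protocol section 7.4. The shifts below are assumptions.

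**1. The SAP's own figures.** The SD of a recording mean is s = 5 × sqrt([1 + 2 rho]/3), which is 3.16 at rho 0.1 and 4.65 at rho 0.8. The normal approximation is n = 2 × (1.96 + 0.84)² × (s/5)².
- rho 0.1: 6.28, so 7.
- rho 0.8: 13.60, so 14.

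The noncentral t with 2n − 2 df gives 8 (power 83.6%) and 15 (power 81.0%). The stated 8 and 15 reproduce, on the premise that the whole 5 points is due to the intervention.

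**2. How a shift could arise.** The estimate has expectation (training effect) + b, where b is the shift between periods.
- Case mix: a 20-point change in the prevalence of a characteristic worth 5 points gives b = 0.20 × 5 = 1 point, or 20% of the planned effect.
- Practice: with two periods of 100 conversations, the midpoints lie 100 conversations apart. A steady gain of 0.01 to 0.025 points per conversation gives b = 1 to 2.5 points.

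**3. Rejection with no training effect.** SE = s × sqrt(2/n); noncentrality = b/SE; unadjusted two-sided 5% test.

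| n per arm | rho | SE | b = 1 | b = 2 | b = 2.5 |
|---|---|---|---|---|---|
| 8 | 0.1 | 1.58 | 9% | 22% | 31% |
| 15 | 0.8 | 1.70 | 9% | 21% | 30% |
| 50 | 0.8 | 0.93 | 19% | 57% | 76% |
| 50 | 0.1 | 0.63 | 35% | 88% | 97.5% |

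The rates rise with n because SE shrinks and b does not.

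**4. Effect of Holm.** Take 16 tests (15 questions and one total, an assumption). The first-step threshold is 0.05/16 = 0.0031. For b = 2.5 the rates become 5.4% (8 per arm), 5.5% (15 per arm), and 37% (rho 0.8) to 82% (rho 0.1) at 50 per arm. Later Holm steps are looser, so the rate under the full procedure lies between these figures and the table.

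**5. Cost of adjustment.**
- One binary factor with average prevalence 50% that shifts by d between periods has correlation d with period, so VIF = 1/(1 − d²). For d = 0.1, 0.2 and 0.3 this is 1.01, 1.04 and 1.10.
- A linear time term beside the period step, with evenly spaced accrual, has correlation 0.866 with period. VIF = 1/(1 − 0.75) = 4, so the SE doubles. Power for 5 points is then 31% at 8 per arm (rho 0.1), 29% at 15 per arm (rho 0.8), and 76% (rho 0.8) to 97.5% (rho 0.1) at 50 per arm. Reaching 80% would take 27 per arm at rho 0.1 and 56 at rho 0.8.

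**The case against.** - **Recruiters are not ignored.** A reader might infer that the models take no account of who held the conversation. The SAP names the recruiter as a source of correlation, states the equal-mean assumption and undertakes to check it and adapt the models. A different recruiter mix in the two periods may therefore be handled. Change within a recruiter over time is not.
- **No shift is shown.** The documents report no drift or case-mix change, and every shift above is assumed. This stands: the claim is that a shift could be reported as effect, not that one will be.
- **The unadjusted rates overstate what the SAP would declare.** This stands in part. At a first Holm step of 16 tests, a 2.5-point shift is declared in about 5% of studies at 8 or 15 per arm. At 50 per arm it is still 37-82%. The bias in the estimate itself does not depend on the threshold.
- **Adjustment is expensive in small samples.** This stands for the time term and for five recruiter terms with 16 to 30 recordings in all. It does not stand for one or two case-mix factors.
- **The covariates may not be available.** The documents do not say that conversation language or antenatal/postnatal timing is recorded for analysis. The eligibility criteria and survey procedures only imply that they are known.
- **This is an openly pre/post feasibility pilot, Figure 3 is titled as a pre/post effect, and Table 1 is a one-line title that might later be split.** All true, and they lower the weight. None supplies the missing comparison or a case-mix or time term.

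**Conclusion.** The point holds in limited form. The models as written name only the intervention, and no listed output compares parents between periods; neither statement rests on an assumed number. Case mix and within-recruiter change over time are uncovered, while differences in mean between recruiters are covered conditionally.

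The size cannot be known from the documents. Under assumed shifts of 1 to 2.5 points and an unadjusted test, false declarations run from about 9% to 31% at the SAP's sample sizes and from 19% to 98% at 50 per arm, and are lower under Holm.

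Two stronger readings are not supported. One is that the reported effect is in fact confounded; no change between periods is documented. The other is that a chance imbalance in a prognostic factor biases the estimate: random variation in case mix is part of the outcome SD and already in the standard error, so only a systematic shift biases the result. The power arithmetic is not at fault. This is a cheap improvement worth making, because the estimate is meant to inform an RCT.

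**What to change.** 1. Split Table 1 by pre and post, within both the approached and the recorded groups.
2. Keep the planned model as primary, but label its estimate a before-after difference.
3. Add one supportive total-score fit adjusted for conversation language and antenatal/postnatal approach, where these are captured. Add recruiter if the number of recordings allows.
4. Add one sensitivity analysis with conversation sequence or calendar time as a linear term.

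The cost is SAP wording, one table split and two extra model fits, with little or no new data collection. The case-mix fit loses little precision (VIF about 1.01 to 1.10 for one binary factor shifting by 10 to 30 points). The time term doubles the standard error, leaving about 30% power for 5 points at 8 or 15 per arm, and it removes only linear drift. It should stay a sensitivity analysis, since a single-site pre/post design cannot fully separate training from time.

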#### 7.4 (P4) Recruitment Discussion (N=100)

**A. Audio-recording and upload (N=100)**

- a. DIVI team has script for consent to audio-record consent discussion**
- b. DIVI team member to retrieve iPad from [redacted]**
  - i. iPad will be passcode protected**
  - ii. Passcode will be provided to consenting DIVI study team members only**
- c. Once the tablet is unlocked, two icons will be present on the home screen**
  - i. Voice Memos app**
  - ii. Link to REDCap**
- d. Using the Voice Memos app**
  - i. Open Voice Memos app**
  - ii. Tap the record button (red circle) to begin recording**
  - iii. Tap the pause button (two vertical red bars) to stop recording**
  - iv. Tap “Done” to save the recording**
  - v. Renaming the recording**
    - 1. Tap the name at the top of the screen (the default name is typically “New Recording X”)**
    - 2. Enter the [DIVI screening ID]**
    - 3. Tap “return” on the keyboard**
    - 4. Tap “Done” on the bottom right corner of the screen**
  - vi. Tap the more options button at the top of the screen (Circle with three dots)**
  - vii. Tap “Share...”**
  - viii. Tap “Save to files”**
  - ix. Tap “On My iPad”**
  - x. Select “BRIEF Consent Audio”**
  - xi. Tap “Save”**
- e. Return to home screen and open link to REDCap survey**
  - i. Enter DIVI screening ID**
  - ii. Select your name from the list of DIVI Team Members**
  - iii. If the Consent Discussion was recorded, select “Yes”**
  - iv. Tap “Upload file”**
  - v. Tap “Choose File”, tap “Choose File” again**
  - vi. Navigate to the “BRIEF Consent Audio” folder**
    - 1. If not in the BRIEF Consent Audio folder already, tap “Browse” in the upper left-hand corner**
    - 2. Tap “On My iPad”**
    - 3. Tap the “BRIEF Consent Audio” file**
    - 4. Tap the recording**
  - vii. Tap “Upload file”**
  - viii. Complete short milestones format survey about consent discussion that just took place**
- f. Close both the Voice Memos and the REDCap link and turn off the tablet**
- g. Return tablet to [redacted]**

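### The SAP pools two independent raters with a third who is not called independent, and its promised check does not name the contrast that matters: a shift of b points in the third rater between periods biases the total-score effect by b/3

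*SAP*

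**What the plan says.** The opening description in the SAP sets up three ratings per recording: "Each recorded recruitment conversation will then be assessed by 3 experts (2 independent, and the member who administered the educational content". It then pools them: "The number of observations will be the number of conversations recorded multiplied by 3 (n_record*3". The expert making the assessment is listed there as one source of correlation, to be handled by GEE. The recruitment conversations themselves are shared among several people: "Conversations will be administered by 6 members, some of whom will administer more conversations than other members".

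The SAP's Analysis Plan fits a linear GEE model to the total score and tests one mean intervention effect. It then admits a rater assumption: "Models above assume each conversation administer has the same mean outcome and that experts evaluate themselves the same as others". The remedy is one sentence: "These two assumptions will be evaluated and GEE models adjusted as needed". It does not say which contrast is examined, what would trigger an adjustment, or what the adjusted model would be. None of the listed tables and figures shows results by rater.

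Neither document mentions masking of raters to period, a mixed scoring order, or an analysis of the two independent experts alone. The protocol has no procedure for the expert ratings and refers to forms on a shared drive (section 9.2). It does have a rating by the recruiter: section 7.4 B asks for Likert answers on 11 milestones, completed straight after the discussion.

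**The concern.** The SAP itself separates the third rater from the two it calls independent. Whether that person is the educator or a recruiter, they would ordinarily know if a conversation took place before or after the training, although the documents do not say so. If that knowledge changes their scoring in the post period, in either direction, the change enters the estimate as an intervention effect or hides one. GEE allows for correlation between ratings; it does not correct a rater whose scale moves between periods.

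This matters more for the estimate than for the test. Section 2 of the protocol wants the pilot to supply effect estimates for planning a later RCT, and a multiplicity correction does nothing for a biased estimate.

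The existing check may miss the problem. Its wording points most naturally to a difference in level between self-ratings and ratings of others. A level difference that is the same in both periods is harmless here. The harmful quantity is the change in that difference between periods.

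**Working it through.** **Inputs.** From the SAP: 3 ratings per recording; equal numbers of recordings pre and post; planned difference 5, SD 5, 80% power, 0.05 level; 8 recordings per arm at intra-recording correlation ρ = 0.1 and 15 at ρ = 0.8. Assumed: a two-sided test, and b, the pre-to-post shift in the third rater's total score relative to the independent experts. The documents give no value for b.

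**Reproducing the plan's figure.** With n recordings per arm, the pooled standard error is SE = SD·√[2(1+2ρ)/(3n)].
- n = 8, ρ = 0.1: 5·√(2.4/24) = 1.58
- n = 15, ρ = 0.8: 5·√(5.2/45) = 1.70

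A noncentral t with 2n−2 degrees of freedom gives power 83.6% and 81.0%, and 8 and 15 are the smallest n that reach 80%. The SAP's sample sizes reproduce.

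**Bias.** With three equally weighted ratings per recording, the period coefficient is the difference in recording means. If only the third rater shifts, the bias is (0 + 0 + b)/3 = b/3.
- b = 2.5: 0.83 points
- b = 5: 1.67 points, one third of the planned 5
- constant offset, b = 0: no bias

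**Which adjustment removes it.** Every recording has the same mix of raters, so rater type is balanced across periods and a rater main effect cannot change the period estimate. In simulated linear GEE fits with b = 3 and no true effect (400 runs per setting), the pooled model gave mean estimates of 0.99 to 1.16, against 1.00 expected. Adding a rater main effect gave identical values. Adding rater type by period brought the independent-expert effect to between −0.05 and 0.15 and recovered b at 2.85 to 3.11.

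**False positives for the total-score test, unadjusted 5% level, noncentrality (b/3)/SE.**

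| Setting | b = 2.5 | b = 5 |
|---|---|---|
| 8 per arm, ρ 0.1, SD 5 | 7.8% | 16.6% |
| 15 per arm, ρ 0.8, SD 5 | 7.6% | 15.7% |
| 8 per arm, ρ 0.1, SD 8 (assumed) | 6.1% | 9.4% |
| 15 per arm, ρ 0.8, SD 8 (assumed) | 6.0% | 9.1% |
| 50 per arm, ρ 0.1, SD 5 | 26% | 74% |
| 50 per arm, ρ 0.8, SD 5 | 14% | 43% |

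The SAP takes its SD from simulated items: "This leads to an approximate distribution of total scores with mean 45 and standard deviation 5". Fifteen independent uniform 5-level items have SD √(15·2) = 5.48, and positively correlated items would have more, so SD 8 is shown as a variation.

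**What the contrast can show.** Third rater minus the mean of the two independents, post minus pre, has SE = SD·√[3(1−ρ)/n]: 5·√(2.7/8) = 2.90 and 5·√(0.6/15) = 1.00. The 95% half-widths are 6.23 and 2.05 points. A 5%-level test of it would detect b = 5 with power 36% in the first setting and 99.8% in the second.

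**If adjustment waited for significance.** Suppose the two-expert result replaces the pooled one only when that contrast has p < 0.05 (60,000 simulated trials per setting, SD 5). At ρ = 0.1 and 8 per arm the false-positive rates are 8.1% (b = 2.5) and 12.9% (b = 5). At ρ = 0.8 and 15 per arm they are 5.8% and 5.0%. The protection depends on ρ, which is not known in advance.

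**Cost of using two experts.** SE = SD·√[(1+ρ)/n]. The variance ratio to three raters is [(1+ρ)/2]/[(1+2ρ)/3]: 0.55/0.40 = 1.375 at ρ = 0.1 and 0.90/0.867 = 1.038 at ρ = 0.8. Power becomes 70.8% at 8 per arm and 79.6% at 15 per arm, SD 5.

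**The case against.** The SAP does not overlook rater differences. It states the assumption and promises to evaluate it, so a reader who inferred that the issue is ignored would be wrong. The safeguard is real but partial: a statistician could follow the sentence to the letter, add a term for rater level, and leave b/3 untouched.

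The harm is conditional. Nothing in the documents says that the third rater shifts, or that raters are unmasked. It is tempting to conclude that the pooled estimate is biased, or that masking was not planned. The text supports neither: b could be zero, and masking could be described in the shared-drive forms.

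The false-positive rates are not the plan's error rate. The plan uses Holm across many tests. With 20 tests assumed, the first Holm step (0.05/20 = 0.0025) gives 1.7% for b = 5 at 8 per arm. Later steps are looser and b would also affect the other tests, so this is a lower bound for that test and 16.6% an upper one. The 74% figure comes from one corner of the range and should not be quoted alone: at 50 per arm it falls to 43% with ρ = 0.8, or 37% with SD 8 and ρ = 0.1.

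The third rater's identity is also open. The opening description reads as the educator; the self-rating wording in the Analysis Plan fits a recruiter. If the third score is the milestone self-assessment in protocol section 7.4 B, it is made right after the discussion and cannot be masked or reordered. Its 11 items are not on the scale of the SAP's approximately 15 questions, so SD 5 and the points scale for b may not carry over. This objection stands, and it is a reason to settle the identity first.

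**Conclusion.** The point holds as a cheap improvement. The SAP pools a rater it does not call independent, describes no masking or mixed scoring order, and promises a check without naming the contrast. A shift of b points between periods biases the linear total-score effect by b/3, and only a rater-type-by-period term or an analysis without that rater removes it. At b = 5 that is 1.67 points of the planned 5.

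This rests on complete, equally weighted ratings and on independent experts who do not themselves shift. It applies to the linear totals and subgroup totals; b/3 does not translate to the question-level odds ratios. The size of b is an assumption throughout.

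A reader might go further and infer that the two-expert analysis must become primary once enough recordings are rated. The documents do not support a threshold for that: it would depend on ρ, which is unknown beforehand, and on an SD of 5 taken from simulated items. Nor would excluding the third rater deal with secular change, which affects all raters in a pre/post design.

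**What to change.** 1. Give the independent experts recordings from both periods under random codes and in random order. The protocol's recording steps (section 7.4 A) name each file by screening ID: "Enter the [DIVI screening ID". Whether that ID reveals the period is not stated. Coding reduces unmasking but cannot hide audible traces of training.
2. Define the Analysis Plan check as a rater-type-by-period contrast, and report it with its 95% confidence interval whether or not it is significant.
3. Always report the total, subgroup and question effects from the two independent experts beside the three-rater analysis. Do not let ρ or a significance test switch the primary analysis.
4. State whether the third rater is the educator or the recruiter, and whether the third rating is the 11-milestone self-assessment. If it is, reconcile its scale with the SAP questionnaire.

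The cost is SAP wording, file relabelling and a few extra rows in the tables; no new raters are needed. The two-expert estimate is less precise: variance rises by 37.5% at ρ = 0.1 and by 3.8% at ρ = 0.8. At the SAP's smaller sample size the contrast will be imprecise (about ±6.2 points), which is why its interval is needed and not only a test result. Rating more recordings would ease both limits, and the protocol heading allows for it: "Audio-recording and upload (N=100".

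### The SAP names no small-sample correction or t reference for its GEE tests; at its own 8 to 15 recordings per arm, routine GEE tests would be too liberal, mainly for the total and subgroup scores.

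*SAP*

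**What the plan says.** The SAP's opening description leaves the number of recorded conversations as n_record, split equally between the two periods. On rating it says: "Each recorded recruitment conversation will then be assessed by 3 experts".

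Under Analysis Plan, single questions are analysed by ordinal logistic regression: "Models will be fit using generalized estimating equations (GEE) to account for correlation among results assessed on the same conversation". For totals and question subgroups the SAP will "use GEE to fit standard linear regression to test the mean effect of intervention". Holm's method is applied across the 15 questions, the totals and the subgroups. The only provision for changing the models concerns two assumptions about means: that recruiters do not differ, and that experts score themselves as they score others. Neither concerns the variance estimator or the reference distribution.

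Under Power calculations the target is stated as "To achieve 80% power at a 0.05 level when the true mean difference is 5 and standard deviation of 5". At an intra-recording correlation of 0.1, "8 videos (with 3 observations) need to be recorded per trial arm", "while 15 recordings are needed per trial arm" at a correlation of 0.8. Protocol 7.4 gives N=100 for audio-recording. The SAP's planned Figure 1 refers to recordings sampled for assessment, so the number rated could be lower than the number recorded.

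**The concern.** All the planned inference comes from GEE with the recording as the independent unit, so the SAP's own sizes mean 16 or 30 clusters. With so few, the usual GEE sandwich standard error is biased downward, and comparing the Wald statistic with the normal distribution adds a second error in the same direction. Both grow in relative terms as the threshold shrinks, and Holm's first steps work at small thresholds.

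What is at stake is the coverage of the reported intervals and the family-wise control that Holm is there to give. Protocol section 2 names effect estimates for a future RCT as an objective, so intervals that are too narrow would carry into later planning. The problem would remain even if recordings by the same recruiter were fully independent.

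**Working it through.** **Inputs.** Difference 5, SD 5, power 80%, level 0.05 (taken as two-sided; the SAP does not say), 8 or 15 recordings per arm and correlation 0.1 or 0.8 (SAP, Power calculations); 3 ratings per recording and equal split (SAP, opening description); N=100 (Protocol 7.4). The number of subgroups is not given. With 0 to 5 assumed, the Holm family has 16 to 21 tests and the first threshold is 0.0031 to 0.0024.

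**1. The SAP's own sample size.** The SD of a recording mean is 5·√((1+2ρ)/3), which is 3.162 at ρ=0.1 and 4.655 at ρ=0.8.
- Normal formula, 2(1.96+0.8416)²·(1+2ρ)/3: 6.28 and 13.60, so 7 and 14 per arm.
- t-test on recording means, df=2n−2: power is 77.5% at n=7 and 83.6% at n=8 (ρ=0.1); 78.1% at n=14 and 81.0% at n=15 (ρ=0.8). This gives exactly 8 and 15.

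The stated sizes therefore match a t-test, which the analysis text does not specify.

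**2. Linear GEE for totals.** With equal clusters and two periods, the sandwich variance equals the usual variance of the difference in recording means times (n−1)/n. The true level of a normal-reference test at level α is therefore

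P(|t with 2n−2 df| > z(1−α/2)·√((n−1)/n)).

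| Per arm | √((n−1)/n) | Level at 5% | CI coverage | Level at 0.05/16 = 0.3125% | Ratio |
|---|---|---|---|---|---|
| 8 | 0.935 | 8.8% | 91.2% | 1.52% | 4.9 |
| 15 | 0.966 | 6.9% | 93.1% | 0.80% | 2.6 |
| 50 | 0.990 | 5.5% | 94.5% | 0.43% | 1.4 |

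With 21 tests the ratios at 8 and 15 per arm are 5.5 and 2.8. Simulation with 100,000 replicates gave 8.8% and 6.7% at the 5% level. A model-based exchangeable standard error does not avoid the problem: 8.2% and 6.5%.

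**3. Where the excess comes from.** With an unbiased standard error but a normal reference, the level is P(|t| > 1.96), which is 7.0% at 14 df and 6.0% at 28 df. At 8 per arm the excess of 3.8 points thus splits into 2.0 from the reference and 1.8 from the standard error. At 15 per arm, 1.9 points split into 1.0 and 0.9. Correcting only the standard error is therefore not enough.

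**4. Ordinal GEE for questions.** These figures come from simulation of proportional-odds models with five equally likely levels, independence working correlation, cluster sandwich and normal reference. At the 5% level the tests ran at about 6.5-8% with 8 per arm and 5.5-6.3% with 15. Near Holm's first threshold they rejected about 2.5-4 and 1.2-1.8 times too often. At 50 per arm they ran at about 5.5%, with a ratio of about 1.

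**5. Family-wise error at Holm's first step.** Simulation of 15 ordinal tests plus one linear total (Monte Carlo SE at most about 0.5 point):

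| Per arm, ρ | Questions independent | Questions correlated (latent 0.5) |
|---|---|---|
| 8, 0.1 | 16.0% | 11.3% |
| 15, 0.8 | 6.8% | 4.7% |
| 50, 0.8 | 5.8% | 3.4% |

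**6. After correction.** For totals, rescaling the standard error by √(n/(n−1)) and using t with 2n−2 df gives 5.0% at any threshold (normal data, equal variances). Interval width changes by √(n/(n−1))·t/1.96: 1.069×2.145/1.96 = 1.17 at 8 per arm, 1.08 at 15 and 1.02 at 50. A similar rescaling with t put the ordinal tests at about 3-4% for nominal 5%.

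**The case against.** The strongest reply is that 16 to 30 recordings are minimum numbers from the power section, not the planned number. Protocol 7.4 gives 100, and at 50 per arm the linear excess is half a point. That stands as far as it goes. But the SAP never adopts 100, speaks of a sample taken for assessment, and justifies its power only at 8 and 15 per arm, so the analysis should be valid there.

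Second, the SAP does not say that it will use an uncorrected sandwich with a normal reference. In the quoted sentence, the word standard describes the linear regression. This also stands: the finding is conditional on routine GEE. The match of 8 and 15 to a t-test may mean that the authors intend a t reference. It cannot prove it, because the SAP pairs simulation with equations and shows neither. But silence leaves the analyst with the usual choice, and both usual standard errors give liberal tests at these sizes.

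Third, this is a feasibility pilot. That limits the consequences, but the SAP still plans formal tests under family-wise control.

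A reader might go further and infer that every test in the family is inflated like the totals, so that the family-wise error would be 1−(1−0.0152)^16 = 22% at 8 per arm and 12% at 15. The SAP does not support this. Fifteen of the tests are ordinal and inflated less, and the total is the sum of the questions, so the tests cannot be independent.

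**Conclusion.** The concern holds in conditional form. If routine GEE Wald tests are used at the SAP's 8 or 15 recordings per arm, tests of totals and subgroups run at about 8.8% or 6.9% instead of 5%, and the question tests are inflated less. Family-wise control is clearly lost near 8 per arm and only modestly affected at 15. If all 100 recordings are rated, the effect is small.

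The documents do not support saying that all 5% tests run at 7-9%, that 16 to 30 recordings is the fixed plan, or that too-small standard errors alone are to blame.

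The figures assume equal clusters of three, normal scores with equal variances for the totals, and no clustering by the six recruiters. Such clustering would make uncorrected tests worse.

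**What to change.** State in the SAP that the linear GEE models for totals and subgroups use one named small-sample corrected sandwich variance, for example Kauermann-Carroll, which is exact for the totals in the balanced case above. Refer tests and intervals to a t distribution with df equal to recordings minus parameters. The t reference is needed as well as the corrected variance: Mancl-DeRouen with a normal reference gives about 5.4% at 8 per arm, but still crosses 0.0025 about 2.4 times too often. For the ordinal models, specify the same approach or a permutation test over recordings. State one number of recordings to be rated, consistent with Protocol 7.4.

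The cost is a few sentences. Linear intervals become about 17%, 8% and 2% wider at 8, 15 and 50 per arm, and the ordinal tests become mildly conservative. No extra recordings are needed: with a t reference the stated 8 and 15 per arm keep 83.6% and 81.0% power for a single test at the 0.05 level.
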